## **2.2 Secondary Objectives**

Additionally, we will determine moderators (caregiver sex, race, child age) and mediators (Self-Determination Theory constructs of autonomy, relatedness, competence; emotional state at ED recruitment) of the intervention effects at 12-month follow-up.

Finally, we plan a cost analysis of the intervention to inform wider dissemination and implementation in settings outside of the ED. We will measure the total costs of the intervention from participant and health system perspectives by gathering estimates of intervention resource requirements, including personnel costs, implementation time, participant time, and material costs. We will calculate costs of the intervention per child. Net costs (savings) will be calculated by subtracting mean costs per participant in the control condition from mean costs per participant who receive the basic TCBD and the enhanced TCBD interventions. We will also estimate cost-effectiveness as measured by dollars per caregiver using a size-appropriate CRS and using the CRS correctly

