## ***3.2 Allocation to Interventional Group***

After completing the baseline survey, all caregivers will be randomized into one of two groups: 1) TCBD intervention group, or 2) control group. Computerized, block randomization (block sizes from four to eight) will be applied to assign eligible caregivers to the TCBD intervention or control group in a 3:1 ratio. Blocks will be stratified by age groups related to child passenger safety recommendations (<2 years – rear-facing CRS, 2-4 years – forward-facing CRS, 5-10 years – booster seat) and the child passenger safety behavior that led to eligibility for study (not using the recommended restraint currently or planning a premature transition in the coming 6 months).

After the 6-month follow-up assessment, caregivers in the intervention group only who continue suboptimal CRS use will be re-randomized by computer in a 1:1 ratio to receive either the basic or enhanced intervention. The enhanced TCBD will include one additional motivational interviewing (MI) session by phone in Month 7/8 and one to two additional tailored text messages in Months 7-12 (total of 7 tailored tips during these months compared to 4 tailored tips for those in the basic TCBD). The extra text messages will be sent to those in the enhanced TCBD group until size-appropriate restraint use is observed. Caregivers receiving enhanced TCBD will be encouraged to obtain a free seat check with a certified child passenger safety technician (CPST) in the community. The primary outcomes (size-appropriate CRS use and CPaSS) will be assessed in-person at Months 6 and 12. The secondary outcome, the CPaSS trajectory, is a measure of correct and consistent restraint use in response to the intervention and will be assessed by scoring photographs submitted by caregivers (Months 1-5; 7-11).

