## 6 Statistical Plan

### 6.1 Sample Size and Power Determination

Briefly, our calculations are based on two-sample comparisons between groups (e.g., control and TCBD) using results from our pilot study that assessed percent size-appropriate child passenger safety behaviors at 6-month follow-up (referred to as the “response rate” below). For analyses involving multiple time points, these calculations represent a conservative lower bound on the power that would only be achieved if the effective sample equals 1 observation per person (i.e. perfect within-individual correlation). For the calculations below we assume: a) 17% response rate among controls; b) 25% response rate among TCBD caregivers at 6 Month (with 75% of TCBD caregivers re-randomized); and c) only 80% of the target sample (n=204 controls and n=516 TCBD in the initial dichotomy) will be available for analysis at follow-up. Components (a) and (b) are based on pilot data where the control group received generic educational materials and outcomes were assessed at 6-months. Component (c) is a conservative correction for attrition. For Aim 2, we estimated power while accounting for uncertainty in the group sizes by simulating response and re-randomization patterns according to the above probabilities and testing for significant between-group differences; this process was repeated 10,000 times and the power was estimated as the percent of replications in which a between-group difference was identified. Binary Outcome: For the binary response case, if the observed response rate is at least 29.4% among those receiving enhanced TCBD, it can be reliably (>80% power) distinguished from a control response rate of 17%. Analogously, a response rate of at least 27.6% among basic intervention would be reliably (>80% power) distinguished from control. Converted to Cohen's  $h$ , both differences reflect small-to-medium effect sizes ( $h = 0.30$  and  $h = 0.26$ , respectively). Numeric Outcome (CPaSS): If the standardized mean difference (i.e. Cohen's  $D$ ) is  $>0.25$  (a small-to-medium effect size), we can reliably distinguish between control and basic TCBD conditions. Similarly, if  $D \geq 0.28$ , a small-to-medium effect size, we will have sufficient power (80%) to distinguish the control and enhanced TCBD conditions. Aim 2: Monte Carlo studies of linear latent trajectory models indicate that a medium level of heterogeneity among the slopes and/or intercepts of the trajectories can be reliably recovered (power  $> 80\%$ ) with a total sample size of  $n=200$ , with power exceeding 95% when the level of heterogeneity is high; given that our sample size soundly exceeds 200, we expect sufficient ability to determine the underlying characteristic trajectory types. Nevertheless, we further justify our sample size with a brief simulation study. Assuming a final sample size of 720, conservatively assuming individuals are only measured at an average of 25% of the 12 monthly assessments, we simulate data from a population with four equally likely trajectory types: consistently low, consistently high, linearly decreasing, and starting high then dropping off. Because we have no basis for estimating variability in the score, we assumed mean/variance equivalence, consistent with the Poisson distribution. Due to the time required to fit such models, we only completed 200 simulation replications, where we were able to correctly conclude (based on BIC) that there were four

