## 6.2 Statistical Methods

All subjects, once randomized, will be included in an intention-to-treat analysis and outcomes will be collected even if the caregiver does not engage in the randomly assigned intervention. We will evaluate randomization by testing for covariate (e.g. demographic characteristics) balance between initial treatment groups, and between the re-randomized treatment groups created after the 6-month follow-up. If significant differences are observed, we will adjust for these variables or conduct stratified analyses. All statistical hypothesis tests and power calculations will use a two-sided = 0.05.

**Aim 1:** To test the efficacy of the TCBD intervention compared to usual care for improving primary outcomes [i.e., size-appropriate restraint (dichotomous) and CPaSS (numeric)] at 12 months. We hypothesize greater proportions of children will be using a size-appropriate restraint and higher CPaSS among caregivers in the intervention groups (basic and enhanced) compared with the control group (usual care) at the 12-month assessment. **Statistical Analysis:** Our primary analytic tool for estimating treatment effects will be generalized linear models (GLMs), and for analyses involving joint analysis of multiple follow-up data points, we will use generalized linear mixed models (GLMMs), which allows direct modeling of the correlations between data points (e.g. repeated measurements on individuals), and the inclusion of individuals with incomplete data (e.g. missing time points). The GLM(M) framework also allows simple controlling for confounders (if necessary) through their inclusion in the model as covariates. For the analysis of binary outcomes, we will use logistic GLM(M)s and for numeric outcomes (CPaSS-D) we will initially specify linear (Gaussian) GLM(M)s; this choice will be scrutinized by analyzing model diagnostics. The primary inferential target will be the coefficient for the treatment group indicator, making this effectively equivalent to ANCOVA. Adjustment for the baseline measurement is important for guarding

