**SubAim:** We will determine moderators (caregiver sex, race, child age) of the intervention effects and mediators (Self-Determination Theory constructs of autonomy, relatedness, competence; emotional state at ED recruitment). We hypothesize that disparities in CRS use can be reduced through a tailored intervention that increases autonomous motivation, competence, and relatedness for correct CRS use. **Statistical Analysis:** **Moderation:** Within the GLM(M) modeling framework described above, we will evaluate moderation by including interactions between treatment group and sex-, race-, and age-based groupings. We will test whether sex as a biologic variable modifies the intervention effect, but will be underpowered to detect differences because children are infrequently with a male caregiver when seeking emergency care (10-15% in our pilot data). **Mediation:** We will use Imai's counterfactual mediation method, a very general framework that takes models for the outcome and mediator as inputs, to estimate mediation effects. Traditional mediation analysis can be susceptible to bias due to model misspecification and design limitations and limitations in the classes of statistical models, that can be accommodated (typically linear regressions for both the mediator and outcome) but the Imai framework can accommodate a wide variety of distributions for both the mediator and the outcome; our initial specification will be a logistic model for the binary variables and a linear (Gaussian) model for the numeric variables. We will use a quasi-Bayesian approach to draw from conditional distribution of the mediator given the "treatment" and other covariates, and that of the outcome given the exposure, mediator, and other covariates, to construct hypothesis tests for the proportion mediated; this approach is robustly implemented in the R package mediation.

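### Section 6.2 tests mediation only through the proportion mediated, whose power is held to about that of the total effect; the indirect effect itself should be the tested quantity

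*Combined protocol and SAP*

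**What the plan says.** Section 2.2 makes it a secondary objective to determine "mediators (Self-Determination Theory constructs of autonomy, relatedness, competence; emotional state at ED recruitment) of the intervention effects at 12-month follow-up". The SubAim in section 6.2 adds a hypothesis about mechanism: the tailored intervention works by raising autonomous motivation, competence and relatedness.

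For the analysis, section 6.2 adopts the counterfactual mediation method, with a logistic model for binary variables and a linear model for numeric ones, both conditional on other covariates. The draws are then used "to construct hypothesis tests for the proportion mediated; this approach is robustly implemented in the R package mediation". No test of the indirect effect is named, testing is not made conditional on a significant total effect, and no rule says when a mediator counts as established. The general rule for tests in section 6.2 applies: "All statistical hypothesis tests and power calculations will use a two-sided = 0.05".

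Section 6.1 gives power for total effects and for the Aim 2 trajectories, but none for mediation. In the SubAim, low power is acknowledged only for moderation by caregiver sex.

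**The concern.** The mechanism question is whether a construct such as autonomy or competence carries part of the effect. That is a question about the numerator of the proportion mediated. The test named in section 6.2 also depends on the denominator, the total effect, which section 6.1 plans to detect with only about 80% power and which is less well powered at the plan's own pilot rates.

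A trial could therefore estimate a clear indirect effect and still return a non-significant mediation test, only because the total effect is imprecise. The interval for the proportion would then often be too wide to interpret. At stake is the answer to a secondary objective; no primary estimate is affected.

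**Working it through.** **Inputs from the documents**
- Section 6.1: "a) 17% response rate among controls; b) 25% response rate among TCBD caregivers at 6 Month (with 75% of TCBD caregivers re-randomized".
- Section 6.1: "only 80% of the target sample (n=204 controls and n=516 TCBD in the initial dichotomy) will be available for analysis at follow-up".
- Section 3.2: those not using a size-appropriate restraint "will be re-randomized by computer in a 1:1 ratio to receive either the basic or enhanced intervention". So enhanced n = 516 × 0.75 / 2 = 193.5, and basic n = 516 − 193.5 = 322.5.
- Section 3.2 also says that computerized blocks will "assign eligible caregivers to the TCBD intervention or control group in a 3:1 ratio". That would give 540:180 of 720 rather than 516:204, so both splits were run.

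**Inputs not in the documents (assumed):** the treatment effect on the mediator (0.15 to 0.4 SD), the share mediated (30% to 80%), and no mediator-outcome confounding.

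**Step 1: reproduce the plan's power.** Section 6.1 says that "a response rate of at least 27.6% among basic intervention would be reliably (>80% power) distinguished from control". Power = Φ[(|p1 − p0| − 1.96·SE0)/SE1].
- Pooled p = (204×0.17 + 322.5×0.276)/526.5 = 0.235.
- SE0 = √[0.235×0.765×(1/204 + 1/322.5)] = 0.0379.
- SE1 = √[0.17×0.83/204 + 0.276×0.724/322.5] = 0.0362.
- Power = Φ[(0.106 − 0.0743)/0.0362] = 80.9%.

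The same formula gives 83.7% for 29.4% v 17% (enhanced). For CPaSS, Φ[0.25/√(1/204 + 1/322.5) − 1.96] = 79.8%, and D = 0.28 (enhanced) gives 79.7%. The stated figures reproduce.

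**Step 2: total-effect power at the plan's 17% v 25%.** The same formula gives 64.5% (204/516), 60.6% (180/540), 58.3% (204/322.5) and 50.0% (204/193.5).

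**Step 3: why the ratio inherits this power.** For draw k let PM(k) = I(k)/T(k), where I is the indirect effect (ACME) and T the total effect. Each quantity has p = 2 × min(share of draws above 0, share below 0). PM(k) is negative exactly when I(k) and T(k) differ in sign. If I(k) is positive in nearly all draws, the share of PM draws below zero equals the share of T draws below zero. The p-value for the proportion is then the p-value for the total effect.

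**Step 4: size.** Simulated trials with a linear mediator model, a logistic or linear outcome model, no covariates, and 1,000 draws per trial (600 trials per binary scenario, 1,000 per CPaSS scenario). Mediator shift 0.4 SD, 50% mediated:

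| Total effect | n control/TCBD | Power, total | Power, proportion | Power, ACME | ACME significant, proportion not |
|---|---|---|---|---|---|
| 17% v 25% | 204/516 | 64.2% | 63.8% | 99.8% | 36.0% |
| 17% v 25% | 204/322 | 56.3% | 56.2% | 99.7% | 43.5% |
| 17% v 25% | 180/540 | 62.0% | 61.5% | 99.0% | 37.5% |
| 17% v 27.6% | 204/516 | 85.3% | 84.8% | 99.8% | 15.0% |
| 17% v 27.6% | 204/322 | 81.0% | 80.2% | 99.7% | 19.5% |
| 17% v 29.4% | 204/194 | 82.8% | 82.0% | 98.7% | 16.7% |
| CPaSS D = 0.20 | 204/516 | 68.3% | 68.3% | 99.9% | 31.6% |
| CPaSS D = 0.25 | 204/516 | 86.9% | 86.8% | 99.9% | 13.1% |
| CPaSS D = 0.25 | 204/322 | 81.9% | 80.7% | 99.0% | 18.3% |
| CPaSS D = 0.28 | 204/194 | 81.4% | 79.8% | 97.5% | 17.7% |
| CPaSS D = 0.35 | 204/516 | 98.5% | 98.4% | 99.9% | 1.5% |

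Monte Carlo standard errors are about 2 points in the first row (√(0.36×0.64/600)) and 1 point at D = 0.25, 204/516 (√(0.13×0.87/1000)). In every scenario run, power for the proportion was at or below power for the total effect.

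**Step 5: what shrinks the gap.**
- *Share mediated 30%:* 34.8% (17% v 25%) and 10.3% (17% v 27.6%), both at 204/516.
- *Weak mediator path, 0.2 SD (CPaSS D = 0.25, 204/516, 50% mediated):* ACME 70.1%, proportion 63.7%, discordant 6.6%. At 0.15 SD the two tests are equal (46.1% and 46.5%), because the mediator path is then the limit.
- *Baseline adjustment (CPaSS, 204/516, 0.4 SD, 50% mediated; baseline correlation assumed):* at D = 0.25 discordance falls from 12.5% unadjusted to 6.7% at r = 0.5 and 1.0% at r = 0.7. At D = 0.20 it falls from 33% to 22% and 9%. The binary outcome was not rerun with adjustment.

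**Step 6: the interval.** With 50% mediated and 204/516, the median width of the 95% interval for the proportion was 0.99 at D = 0.25 and 1.58 at D = 0.20. In separate binary runs (17% v 25% or 27.6%, shift 0.25 to 0.5 SD, 30-50% mediated) the interval reached above 100% in 38-79% of trials.

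**The case against.** The strongest reply is that the plan does not exclude the ACME. Section 6.2 adopts the method in order to estimate mediation effects, and the same procedure produces the ACME. A reader might infer that real mechanisms will often be declared absent. The documents do not support that: they state no rule by which a mechanism is declared present or absent, and how often the two tests disagree depends on inputs they do not contain. Nor does the interval for the proportion usually pass 100%; in 38-79% of trials, often is the fair word.

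Second, section 6.2 adjusts a single follow-up for baseline and lets the mediation models include covariates, so the unadjusted figures overstate the loss for CPaSS. This stands, and Step 5 shows the reduction.

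Third, the large gaps need a fairly strong mediator path, and all runs assume no mediator-outcome confounding. This also stands. The proportion uses the same indirect effect as its numerator, so it does not escape that confounding.

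Fourth, asking what share of an established effect a construct explains is a coherent question, and the ratio test errs towards caution rather than towards false mechanisms. But the plan does not restrict the test to an established effect. If that condition is intended, it should be written down rather than left to the behaviour of a ratio.

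These points limit the size and the severity. They do not change the fact that the only named test is held to the power of the total effect.

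**Conclusion.** The point holds in a limited form. That the ratio test has essentially no more power than the total-effect test follows from the sign argument and appears in every scenario run.

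The size is conditional. With a 0.4 SD mediator shift, 50% mediated and unadjusted models, the ACME is significant and the proportion is not in about 35-45% of trials at 17% v 25%, about 13-20% at the plan's 80%-power thresholds, and very few when the total effect is large. It is smaller for CPaSS with baseline adjustment and smaller when the mediator path is weak. The 25% is a 6-month pilot rate, while the mediation question concerns 12 months, so the relevant total effect may differ.

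Severity is low: this is a secondary SubAim, and no primary estimate or sample size depends on it.

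**What to change.** In the mediation paragraph of section 6.2, make the ACME the tested quantity, with its 95% interval: a risk difference for size-appropriate restraint use and points for CPaSS, from the same baseline-adjusted models and the same R package. Report the proportion mediated with its interval as descriptive only, and only where the total effect is clearly non-zero, for example where its 95% interval excludes zero.

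The cost is a sentence or two of wording, with no new data, models or software. The change should be made before the 12-month outcomes are analysed. One run of the procedure yields both results, and naming the tested quantity in advance removes any choice between them afterwards.

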## 3.4 Study Endpoints

### 3.4.1 Primary Study Endpoint

The primary outcomes (size-appropriate CRS use and CPaSS) will be assessed in-person at Month 12. The secondary outcome, the CPaSS trajectory, is a measure of correct and consistent restraint use in response to the intervention and will be assessed by scoring photographs submitted by caregivers (Months 1-5; 7-11) and collected by the study team (Months 6 and 12). Photographs will be scored using the CPaSS tool by research team members blinded to the treatment group.

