#### 5.1.2 Visit 2 –Monthly photo requests (over 12 months of study enrollment)

Over the course of the study, all study participants will receive 8 photo requests in months 1, 2, 3, 5, 7, 8, 10, and 11 via text message from the study that asks for them to send us back digital photographs of how their child usually travels in their vehicle. Participants can complete a total of 8 photo requests over the course of the study and will be paid for completing each of them. The CPaSS measure will be used to assess all digital photographs and incorporates elements of seating position, mode selection, CRS fit, and CRS use/misuse drawn from AAP Guidelines and standardized error severity scores for child restraints.

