**Aim 2:** To use latent growth curve models to identify characteristic trajectories for the CPaSS observed in digital photographs over the 12 study months and assess for correlates of the trajectory types. We hypothesize that caregivers will have different CPaSS trajectories in response to the basic intervention, the enhanced intervention, and the control condition. We expect to identify at least four patterns of response. **Statistical Analysis:** We will determine 12-month CPaSS trajectory types using adaptations of finite mixture models for the case where the units are trajectories. We will define trajectory shapes through methods combining semiparametric regression modeling (e.g., generalized additive models), with latent class regression, using the R package flexmix. Following convention, we will use the Bayesian Information Criteria (BIC) to determine the appropriate number of latent classes, while also making practical considerations to avoid overfitting, such as not allowing overly small groups to be created, as in previous applied work. Using the posterior probability of class membership, we place individuals into trajectory groups and treat that grouping as the outcome in a subsequent multinomial regression model to determine correlates of class membership, including treatment group, caregiver race/ethnicity, and child age group. If substantial uncertainty in class membership is found, outcomes in the multinomial model will be weighted accordingly.

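### Aim 2: testing 12-month CPaSS trajectory class across basic, enhanced and control compares groups sorted on Month-6 restraint use, so the test can exceed its 5% level with no treatment effect

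*Combined protocol and SAP*

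**What the plan says.** Section 6.2, Aim 2, gives a hypothesis about three conditions: "We hypothesize that caregivers will have different CPaSS trajectories in response to the basic intervention, the enhanced intervention, and the control condition". The outcome covers the whole study: "We will determine 12-month CPaSS trajectory types using adaptations of finite mixture models". Each caregiver is placed in a class, and a multinomial model is used "to determine correlates of class membership, including treatment group, caregiver race/ethnicity, and child age group". The plan does not say whether treatment group there has two levels (initial arm) or three.

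Section 3.2 fixes who can receive enhanced TCBD. After the 6-month assessment, "caregivers in the intervention group only who continue suboptimal CRS use will be re-randomized by computer in a 1:1 ratio". TCBD caregivers who use a size-appropriate restraint at Month 6 stay in basic, and controls are not sorted.

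Section 5.1.2 says CPaSS "incorporates elements of seating position, mode selection, CRS fit, and CRS use/misuse", and places the eight photo requests in Months 1, 2, 3, 5, 7, 8, 10 and 11. Sections 3.2 and 3.4.1 differ on whether Month 6 belongs to the trajectory. Section 3.2 lists only Months 1-5 and 7-11; Section 3.4.1 gives "Months 1-5; 7-11) and collected by the study team (Months 6 and 12".

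**The concern.** The three conditions were not created by one randomisation. TCBD and control were. Enhanced and basic were randomised against each other only within the Month-6 non-users of the TCBD arm. Pooling that arm's Month-6 responders into basic gives three groups that differ in Month-6 restraint use before enhanced TCBD has done anything.

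Two features carry this difference into the Aim 2 outcome. CPaSS scores mode selection, so Month-6 use and the CPaSS trajectory are likely to be related. And four of the eight photo requests fall before Month 6, so enhanced TCBD cannot have influenced them.

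At stake is what a positive Aim 2 result means. A class-by-group association could reflect who was eligible for re-randomisation and not what the interventions did. It would also lean one way: fewer good trajectories in enhanced, more in basic.

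**Working it through.** **1. Group sizes (Section 6.1).** Analysable: 204 control and 516 TCBD, with 75% of TCBD re-randomised.
- Re-randomised: 0.75 × 516 = 387; enhanced = 387/2 = 193.5.
- Basic with responders pooled in: 516 − 193.5 = 322.5, of whom 516 − 387 = 129 are responders.

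**2. The plan's own power figure.** It claims more than 80% power for basic 27.6% v control 17%. With a pooled null variance and two-sided 0.05:
- n = 204 and 322.5: pooled rate 0.2349, null SE 0.0379, alternative SE 0.0362. Then (0.106 − 1.96 × 0.0379)/0.0362 = 0.87, power 0.81. Reproduced.
- n = 204 and 193.5 (re-randomised basic only): SEs 0.0417 and 0.0415, z = 0.59, power 0.72. Not reproduced.

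So the plan's sizing treats all Month-6 responders as basic.

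**3. Sorting with no treatment effect.** If 25% of every arm are users at Month 6, users make up 25% of control, 129/322.5 = 40% of basic and 0% of enhanced. At 17%, responders number 0.17 × 516 = 87.7 and enhanced is 0.83 × 516/2 = 214.1. Users are then 17% of control, 87.7/301.9 = 29% of basic and 0% of enhanced.

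**4. Effect on class shares.** Take the four equally likely classes of Section 6.1 and assume a Month-6 odds ratio of 10 for the high v the low class. At 25% use, the class probabilities of use are low 0.099, high 0.524, decreasing 0.278 and drop-off 0.099. Each class has 516/4 = 129 TCBD caregivers.

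| Class | Control | Enhanced: 0.25(1 − p)/0.75 | Basic: remainder/322.5 |
|---|---|---|---|
| High | 25% | 0.25 × 0.476/0.75 = 15.9% | (129 − 30.7)/322.5 = 30.5% |
| Low | 25% | 0.25 × 0.901/0.75 = 30.0% | (129 − 58.1)/322.5 = 22.0% |

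**5. Rejection rates with no treatment effect.** The link, class means and curve shapes are assumptions.

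First set-up: Poisson scores, assumed class mean levels 4 to 10, scores other than Month 6 observed with probability 25% or 80%, most probable class assigned using the true class means, odds ratios 3.3, 11 and 37, 600 replicates. The three-group test rejects 11–69% at 17% use and 17–95% at 25%. The initial-arm test rejects 3.5–6.2%.

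Second set-up: Poisson means 3 (low) and 9 (high), drop-off after Month 4, each month observed with probability 25%, classes fitted by EM, likelihood-ratio test of class by group, 2,000 replicates:

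| Odds ratio | Three groups, 25% use | Three groups, 17% use |
|---|---|---|
| 1 (no link) | 5.2% | – |
| 4 | 26% | 16% |
| 10 | 66% | 37% |

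At odds ratio 2 and 25% use the rate is about 11% (600 replicates). With classes known exactly and no link, the rate is about 5% at either level of use.

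Variations at 25% use:
- Month 6 left out of the trajectory: 24% (odds ratio 4) and 61% (odds ratio 10).
- Enhanced v control alone: 13% and 30%.
- 180/540 instead of 204/516 (odds ratio 10): 68%.

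**6. Contrasts that follow the randomisations.** Initial arm: 4.6–5.3%. Enhanced v basic among re-randomised caregivers, on 12-month classes: 4.2–5.4%.

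Embedded strategies v control, with weight 2 for re-randomised caregivers and weight 1 for responders: 5.2–5.6% for the enhance strategy and 5.2–6.2% for the continue-basic strategy (3,000 replicates, known classes). The weights undo the sorting in step 4: high-class responders 129 × 0.524 = 67.6, plus 2 × 30.7 = 61.4, give 129.0 of 516, or 25%.

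**The case against.** The strongest reply is that the three-level test is inferred. Section 6.2 does not define treatment group, and its opening paragraph distinguishes initial from re-randomised groups. Coded as initial arm, the model holds its level. That is correct, but a two-level model would not test the stated three-condition hypothesis. The hypothesis and the sizing in step 2 both point to three levels, so the text needs settling either way.

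Four further points stand in whole or part:
- Month-6 non-use decides eligibility for enhanced TCBD, not assignment to it. Among the re-randomised, enhanced v basic is a fair comparison, even on 12-month classes.
- Whether Month 6 is in the trajectory is unclear. Leaving it out lowers the inflation only slightly.
- With no effect, 17% is the more natural rate of use, because the plan's 25% already contains a TCBD benefit. The lower range then applies.
- Sections 3.2 and 3.4.1 call the trajectory secondary, although Section 2.1 lists it under primary objectives. Efficacy is tested in Aim 1, so a decision to drop the enhancement because of Aim 2 is conjecture.

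The safeguards in Section 6.2 do not remove the problem. Its balance checks compare the initial arms and the re-randomised groups, so neither sets enhanced against control. The weighting described for Aim 2 is for uncertain class membership.

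**Conclusion.** The concern holds on the three-level reading. If Month-6 use is related to trajectory class, the test exceeds 5% under no effect, and enhanced looks worse than basic through selection. The mechanism and its direction follow from Sections 3.2, 5.1.2 and 6.2, given that link. The size does not: roughly 11–69% at 17% use and 17–95% at 25% with estimated classes, and about 5% without a link.

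A reader might infer that the test is bound to reject whatever TCBD does. The documents do not support that: they give no figure for the link, and under weaker links the rate stays far below certainty. A reader might also infer that basic and enhanced cannot be compared with control over 12 months. Weighted embedded strategies allow that comparison.

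**What to change.** In Section 6.2, Aim 2, define treatment group and do not test class against a three-level group that pools Month-6 responders into basic. Instead:

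- (a) Regress 12-month class on the initial randomised arm (TCBD v control).
- (b) Compare enhanced with basic only among caregivers re-randomised at Month 6, adjusting for Month-6 CPaSS. A Months 7–12 trajectory is an optional, sharper estimand and is not needed for error control. At the plan's 25% measurement density it leaves about 0.25 × 6 = 1.5 scores per caregiver.
- (c) If basic or enhanced is to be compared with control, compare the embedded strategies (TCBD then continue basic if a non-user; TCBD then enhance if a non-user) with control. Use weight 2 for re-randomised caregivers, weight 1 for Month-6 responders, and robust standard errors.

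Reword the hypothesis to these contrasts, and reconcile Sections 3.2 and 3.4.1 on Month 6. The cost is some extra analysis and less precision for the enhanced contrasts; no new data or participants are needed.
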